Research Intervention(s)/Interactions	For the main study, parents attending a well child visit with their child (4 and 12 months) will be played a ~3 min video while waiting in the exam room and will be asked questions about their perception of the video. When parents return for their next scheduled well-child visits during the study at 6, 9, or 15 months they will be asked to complete a short survey about infant feeding practices. Parents who participate in the study during the first months of the study will be the control group. Those who participate after the sugary

Protocol Title: Well-Child Visit Video Project

	
beverage reduction videos are introduced will comprise the intervention group.
 
A subsample of parents attending their child's 4 or 12-month well-child visit will be invited to participate in a long-term follow-up sub-study. This will include completing a knowledge and practice survey, watching a short video, and completing a video perception survey at baseline. In addition, they will be asked to complete a short survey during their next well-child visit (if they attend Hughes Spalding clinic for this), and by email or text approximately 5 months later. (PHI in the form of first name and email address or phone number for text will be collected).
 
In addition, clinic staff will be interviewed about their perceptions of the usefulness and ease of the videos (no PHI will be collected from staff).

Study Population	Parents of children age 4-15 months at enrollment who attend a well-child visit at the collaborating pediatric primary care clinic during the pilot implementation.
Sample Size	Main parent study: up to 750 total (estimated 375 in each of the two groups). Long-term follow-up: up to 100 parents (30 in each of the two groups). Clinic staff interviews: 6-10 staff
Study Duration for individual participants	Parents in the main study: estimated max total 10 minutes Parents in the long-term follow-up subsample: estimated total 20 minutes. Clinic staff: 5-30 minutes.

Study Specific Abbreviations/ Definitions	SCB: sugar-containing beverages; T2D: Type 2 diabetes; Well-child visit: regularly scheduled preventative healthcare visit for children under the age of 18.
Funding Source (if any)	The Global Center for Diabetes Translation Research, pilot grant program (original funding from NIH).

2. Objectives

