1) parents viewing a ~3-minute video during routine 4-month or 12-month well-child visits and completing a survey about their perception of the video afterwards. The control group will view an educational video about a topic other than infant SCB consumption. This will be done in the first months of the study. The intervention group will include those parents who participate in the study after the control data has been collected and two SCB reduction-related videos have been introduced (one for showing at the 4-month visit and one for the 12-month visit).

2) parents attending a 6-month or 15-month well- child visit will be asked to complete a survey to assess infant feeding practices.

A sub-sample of parents who consent to participate in a long-term follow-up component of the study will complete a child feeding knowledge and behavior survey at the enrollment clinic visit (4-month or 12-month well-child visit). In addition, they will view a short video (~ 3 minutes) and answer a few questions about their perception of the videos. They will be asked to complete another knowledge and behavior survey at their child's next well-child visit at 6 and 15-months, and by e-mail 4-5 months after enrollment. The control group will be comprised of parents enrolled prior to the introduction of the intervention videos.

In addition, clinic staff involved in providing well-child care will be invited to participate in key informant interviews to learn from them how they how they perceived the process of integrating the videos into practice, the parent response to the videos, and whether or not they perceive them to be a valuable tool.

6. Procedures Involved

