- 3) Parent/caregivers who are not able to communicate in English

We will not be targeting a specific community or racial/ethnic group in this study.

11. Local Number of Participants

The total number of participants for the study will be 50-54 participants. For the main part of the study with parents, we will have at least 44 parents (22 parents in each of the two groups). The long-term follow-up participants are a subsample of the 44 parents and will include 20 parents (10 from each of the two groups). For the clinic staff interviews, 6-10 staff participants will be included.

12. Recruitment Methods

Participants for the main study will be recruited while attending a well-child visit at the Hughes Spalding clinic during the study period. The clinic staff that escorts parents and their children from the main waiting room to the exam room will ask parents if they are willing to participate in the study. All parents over the age of 18 years with the cognitive and language ability to respond to the survey question in English will be invited to participate. As this activity will be integrated into and offered to parents of all children attending the selected well-child visit, no payment will be provided

Parents participating in the sub-sample will be recruited by clinic staff who will inform them about the study. Name and contact information will be collected then. This will be conveyed to the research team who will follow up to do an informed consent. The

parents will be provided a \$10 Amazon gift card for each follow-up interview completed. These will be sent electronically following the completion of the final survey.

13. Withdrawal of Participants

We do not anticipate withdrawing any participants from the study without their consent.

14. Risks to Participants

Potential risks to the long-term follow-up subsample of participants are the loss of confidentiality and the time spent for the follow-up survey phone call. The risk of loss of confidentiality will be minimized by using study IDs and saving identifying information on password protected computers, to which only select study staff will have access.

A potential risk for clinic staff in participating in the study is loss of productivity while working at the clinic. Loss of productivity will be minimized by giving staff the choice to not participate and if they decide to participate, they will decide how much time they would like to be engaged (from 5 to 45 minutes).

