We do not anticipate any unforeseeable risks to study participants.

15. Potential Benefits to Participants

There will be no direct benefits to parent participants other than the possibility of increased knowledge regarding healthy child feeding which could result in improved practices with their child. The benefit to clinic staff will be in knowing that they contributed to efforts to improve patient care and clinic work flow and the food we provide to them at the clinic to thank them for their time.

The parents in the long-term follow-up subsample will be compensated for their time via a \$10 Amazon gift card for completion of the final survey. These will be sent electronically following the completion of the surveys.

16. Data Analysis, Management and Confidentiality

Study IDs will be used to identify parents enrolled in the long-term follow-up study and only the PI will be able to link the ID to the personally identifying data. Data will be stored on a password protected computer.

Sample size. Previous studies estimate that 47.7% (SD=3.2) of children age 6-11 months drink 100% fruit juice. Fewer, 13.6% (SD=2.0) drink sugar-sweetened beverages¹². We determined that a sample size of 44 per group will provide 80% power to detect a significant difference ($p<0.05$) if the prevalence of SCB consumption is 48% among infants in the control group and 20% among those in the post-intervention group. Participation of 49 parents in the intervention group will allow for a final sample of 44 assuming a 10% drop-out.

Data analysis. Descriptive statistics will be used to describe the sample and to compare the SCB-related knowledge, perceptions and practices of parents who received the intervention compared to those who did not. Chi-squared tests will be used to compare the prevalence of SCB-related practices between the control group and the intervention group. Any demographic differences between the pre and post cohorts will be assessed and controlled for using stratified analyses or multivariate models. A p-value of 0.05 will be used to determine statistical significance. All statistical analysis will be conducted using SAS 9.4 (Cary, NC). Key themes arising from the discussions with key informants will be summarized.

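### The sub-study collects each parent's own knowledge and practice answers at enrolment in both sequential cohorts, but Section 16 names no effect estimate that uses them

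*Combined protocol and SAP*

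**What the plan says.** Section 5 (Study Intervention / Design) says that sub-study parents "will complete a child feeding knowledge and behavior survey at the enrollment clinic visit", then again at the next well-child visit and by e-mail 4-5 months after enrolment. The groups are sequential: "The control group will be comprised of parents enrolled prior to the introduction of the intervention videos".

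The Study Summary lists the enrolment steps in this order: "This will include completing a knowledge and practice survey, watching a short video, and completing a video perception survey at baseline". Section 6 and Appendix A list the survey ahead of the video too, and Appendix A does so for both cohorts. Answers can be linked within parent: "Study IDs will be used to identify parents enrolled in the long-term follow-up study" (Section 16). Section 6 gives the sub-study a longitudinal purpose that includes possible impact on knowledge and practices.

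Section 16 is the only analysis text. Besides descriptive comparison of the groups it says: "Chi-squared tests will be used to compare the prevalence of SCB-related practices between the control group and the intervention group", and "Any demographic differences between the pre and post cohorts will be assessed and controlled for using stratified analyses or multivariate models". It has no separate analysis for the sub-study.

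The main study differs. At the 4- and 12-month visits its parents answer only questions about the video, so it has no baseline knowledge or practice answer.

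**The concern.** The Study Summary labels the design as controlled before-and-after, and the sub-study is the only parent component with a before measurement on the same person. Yet none of the named tests or adjustments draws on it. Prior juice knowledge or practice is not a demographic characteristic, so the stated adjustment does not reach it.

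Two things are at stake. First, bias: without randomisation, a cohort difference already present at enrolment can be read as a video effect to the extent that it lasts. Second, precision: where the baseline answer predicts the follow-up answer, leaving it out gives away information from a small sample.

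The choice of estimator is also left open. Unadjusted, adjusted and change-based estimates can differ by several points on the same data, so the choice should be made before the data are seen.

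**Working it through.** **1. The plan's own figure.** Inputs from Section 16: 48% against 20%, 80% power, p<0.05, 10% drop-out. Two-sided pooled formula without continuity correction, with mean proportion 0.34:

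n = [1.96·√(2·0.34·0.66) + 0.842·√(0.48·0.52 + 0.20·0.80)]² / 0.28² = (1.313 + 0.539)² / 0.0784 ≈ 43.7, so 44. Then 44 / 0.9 = 48.9, so 49.

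Both stated figures reproduce. The formula is for an unpaired comparison with no baseline term.

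**2. Bias.** Let *gap* be the cohort difference at enrolment, *k* the share of it that persists to follow-up, and *d* the within-group slope of follow-up on baseline. With no video effect, and the later cohort starting with less juice:

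- unadjusted: −k × gap
- baseline-adjusted: (d − k) × gap
- difference in change: (1 − k) × gap

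A negative value favours the video. The documents give none of gap, k or d. For a 10-point gap and d = 0.5, in percentage points:

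| Persistence k | Unadjusted | Adjusted | Change |
|---|---|---|---|
| 0 | 0 | +5 | +10 |
| 0.5 | −5 | 0 | +5 |
| 1 | −10 | −5 | 0 |

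Adjustment gives a smaller bias than no adjustment when |d − k| < k, that is when k > d/2. The worst adjusted error over k = 0 to 1 depends on the slope. It is 5 points at d = 0.5, 7 at d = 0.3 or 0.7, and 9 at d = 0.1.

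**3. False positives of the unadjusted chi-squared test.** Simulated with no video effect, d = 0.5, k = 1, at 30 / 50 per group. The Study Summary gives 30 per group; 50 is half of its maximum of 100.

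| Setting | Gap | Bias | False positives |
|---|---|---|---|
| Outcome at 48% in all parents | 10 | −10 | 12% / 18% |
| Juice practice, half 4-month enrollees | 10, in 12-month enrollees only | −5 | 7% / 9% |
| Juice practice, half 4-month enrollees | 20, in 12-month enrollees only | −10 | 12% / 18% |

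The 48% derives from the plan's estimate for the share "of children age 6-11 months drink 100% fruit juice" (47.7%), so using it at enrolment is an assumption. The mixed setting assumes 5% juice at the 4-month visit, where a fall of 10 or 20 points is impossible, and 48% at follow-up in controls. Half the parents carry the gap, so the bias halves.

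**4. Precision, no gap, 30 per group.** The ratio of adjusted to unadjusted variance is 0.92, 0.76 or 0.52 at correlation 0.3, 0.5 or 0.7. Difference in change gives 1.38, 1.00 or 0.60, so it never does better than adjustment here. For juice practice in the half-and-half mix, the adjusted ratio is 0.964 (slope 0.3) or 0.869 (slope 0.5). Since 30/0.964 = 31.1 and 30/0.869 = 34.5, 30 parents act like about 31 to 35.

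**5. If the survey came after the video.** Suppose a 20-point knowledge effect already showed in full at that survey. With d = 0.5, adjustment would report 20 − 0.5 × 20 = 10 points, and difference in change 20 − 20 = 0. The order therefore matters.

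**The case against.** The strongest reply is that Section 16 simply does not specify a sub-study analysis. Its descriptive comparison could include baseline answers by cohort, and its multivariate models do not exclude a baseline term. This stands. A reader might infer that the plan discards the baseline; the text supports only that no named effect estimate uses it.

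A second reply is that no gap has been shown. Both cohorts come from one clinic, at the same visit ages, a few months apart. This also stands: the figures show what a gap would do, not that there is one.

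Third, the larger error rates do not carry over to juice practice. Taking 48% for every parent, a fully persisting 20-point gap would give −20 points and 35% / 55% false positives. That ignores the 4-month enrollees; with half the parents enrolled at 4 months the figures are −10 points and 12% / 18%.

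Fourth, the survey is already listed before the video. That is right, but listing is not a requirement. Section 12 says of parents' contact details: "This will be conveyed to the research team who will follow up to do an informed consent". This leaves the timing of consent relative to the video open.

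Finally, this is a pilot and the sub-study is its smaller part. That limits the weight of the point, but the remedy is correspondingly cheap.

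**Conclusion.** The point holds as an omission in the sub-study analysis. Both cohorts supply a linkable baseline answer, the comparison is not randomised, and the named methods give that answer no role in estimating the effect.

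On assumed inputs (slope 0.5, gap fully persisting), the bias avoided in part is 5 to 10 points in the settings shown, with false-positive rates of 7% to 12% at 30 per group and 9% to 18% at 50. The precision gain is small for juice practice and worthwhile for knowledge only if the correlation is about 0.5 or more. It is also an inference that the survey asks about juice specifically; Section 6 describes its content as sugar-containing beverage knowledge and feeding practices.

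Three stronger conclusions are not supported. Adjustment does not remove confounding in general: it is unbiased only if follow-up depends on cohort solely through the baseline answer. It is not best in every case: it adds bias if the gap has gone by follow-up, and its margin over the other estimates depends on the slope. Nor does it help the main study of up to 750 parents, which remains an after-only comparison of sequential cohorts. Calendar trends after enrolment remain under every estimator.

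**What to change.** In Section 16:

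- State that the primary sub-study effect on each follow-up juice-knowledge and juice-practice answer comes from a model with group, the same parent's baseline answer and enrolment visit (4 or 12 months), with a penalised or small-sample version if events are sparse.
- Report baseline answers by cohort.
- Give difference in change as a sensitivity analysis only, noting that it is unbiased only if the gap persists fully.
- State that calendar trends after enrolment remain, and that the main study is an after-only comparison of sequential cohorts.

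In Sections 5 and 6, state that the enrolment survey is completed before the video.

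The cost is wording and a little more analysis; no new data are needed. The drawback is possible model instability. At the plan's assumed 20%, 30 intervention parents give about 30 × 0.20 = 6 who give juice, before drop-out. Section 11 still shows 10 per group, which would give about 2, so the sub-study size should be reconciled at the same time.

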Videos have previously been shown to be a low-cost and effective way of conveying key educational message to a variety of audiences²³. Our recent 3-month pilot study in a large pediatric primary care clinic demonstrated that the viewing of a short educational video (on a variety of topics) during each well-child visit, newborn to age 3, was well-received by both parents and healthcare providers. Nearly all (98%) parents who completed a post-video survey (n=67) reported that they liked it, 88% reported that viewing it while waiting to see the doctor was a good use of their time²⁴, and healthcare team collaborators valued them so much they requested to continue using them after the pilot study was concluded. Building upon this work, the goal of the proposed pilot project is to assess the impact of using targeted, age-specific videos during well-child visits as a tool for increasing parent compliance with feeding practices that promote a reduction in children's SCB

consumption.

The results of this study will be used to inform a randomized control trial to test the impact of a comprehensive program designed to strengthen the early feeding/diabetes prevention related education and counseling provided by pediatric primary care providers. The program to be tested will center around an on-going, evidence-informed program^{25,26} which will, dependent on the results of this pilot, be expanded to include the use of videos.

4. Study Endpoints

The primary outcome will be the percentage of parents who a) are aware of infant fruit juice consumption recommendations and b) who report that they do not give their young children fruit juice.

Secondary outcomes will include 1) the percentage of clinic staff who report that the SCB consumption related videos were easy to incorporate into the flow of clinic operations and 2) the percentage of parents who viewed an intervention video report that they enjoyed it or learned something from it

We will also explore to determine if viewing the short (3-4 minute) educational videos on recommended infant feeding practices played during well-child visits have an impact on other (non SCB-related) infant feeding practices .

No risks to study participation are anticipated.

5. Study Intervention / Design

The main study will involve:

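### Section 16 does not require adjustment for survey visit (6, 9 or 15 months); stratifying by visit would cheaply protect the juice comparison if the visit mix differs between periods

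*Combined protocol and SAP*

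**What the plan says.** The primary practice outcome (Section 4) is the percentage of parents "who report that they do not give their young children fruit juice". Section 16 gives the test: "Chi-squared tests will be used to compare the prevalence of SCB-related practices between the control group and the intervention group". The only adjustment it describes is: "Any demographic differences between the pre and post cohorts will be assessed and controlled for using stratified analyses or multivariate models". It names no visit stratum and does not say whether surveys from different visits are pooled.

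The surveys come from children of quite different ages. Section 1 says of parents returning for their next "well-child visits during the study at 6, 9, or 15 months they will be asked to complete a short survey". Section 6 and Appendix A also list 6, 9 and 15 months. Section 5 lists only 6 and 15 months for the main-study survey.

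The one juice prevalence cited is "47.7% (SD=3.2) of children age 6-11 months drink 100% fruit juice", which is probably the source of the control rate in the sample-size condition: "if the prevalence of SCB consumption is 48% among infants in the control group and 20% among those in the post-intervention group". No figure is given for 15 months. Section 6 nevertheless justifies the choice of visits partly by a steep second-year rise in juice and other sugary intake. The current size in Section 1 is "Main parent study: up to 750 total (estimated 375 in each of the two groups").

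**The concern.** The two cohorts are recruited one after the other, so nothing in the design balances the ages at which parents are surveyed. By the plan's own account, age is likely to be prognostic for juice use. If surveys are pooled, relatively more 15-month surveys in the intervention period would hide a benefit, and relatively fewer would exaggerate one.

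The estimate matters as well as the p-value, because Section 3 states: "The results of this study will be used to inform a randomized control trial". Leaving the choice between pooled, stratified and model-based results until differences have been seen also leaves an analysis decision open that could be closed now.

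**Working it through.** **1. The plan's own figure.** Mean rate (0.48 + 0.20)/2 = 0.34. For two-sided 0.05, 80% power and no continuity correction:

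n = [1.96√(2 × 0.34 × 0.66) + 0.842√(0.48 × 0.52 + 0.20 × 0.80)]² / 0.28² = (1.313 + 0.539)² / 0.0784 = 43.7, so 44 per group. Then 44/0.9 = 48.9, so 49.

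Both stated numbers reproduce. The calculation is for one pooled, unstratified comparison with a single control rate.

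**2. Shift from visit mix, with no video effect.** Shift = sum over visits of (intervention share − control share) × juice prevalence.

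- *Assumed imbalance.* Prevalence 47.7% at 6 and 9 months (the plan's figure); 55 / 60 / 70% at 15 months (assumed); control visits in equal thirds; intervention 15-month share 42% (assumed). Shift = (0.42 − 0.333) × (7.3 / 12.3 / 22.3) = 0.6 / 1.1 / 1.9 points.
- *Appendix A calendar alone.* Survey months for 6/9/15 months are 3:3:3 in control and 3:2:3 in intervention. At equal monthly flow the largest shift is (0.375 − 0.333) × 22.3 = 0.9 points. It is 0 if prevalence is linear over the three visits (30/50/70%) and about ±0.8 if curved (25/55/65% or 35/45/75%).
- *Ten points moved from 15-month to 6-month surveys (assumed).* 0.10 × (40 − 56) = −1.6 points for a 40/48/56% gradient; 0.10 × (30 − 70) = −4.0 points for 30/50/70%.

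**3. Effect on the test.** Simulation of 40,000 trials per scenario, 375 independent surveys per group, common odds ratio across visits, two-sided 0.05. CMH is the Cochran-Mantel-Haenszel test by visit. The conditional method uses CMH only when visit differs between groups at p<0.05.

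| Quantity | Method | 55% | 60% | 70% |
|---|---|---|---|---|
| Type I error, share 42% | pooled | 5.8% | 6.2% | 8.6% |
| | conditional | 5.2% | 5.2% | 5.6% |
| | CMH | 5.0% | 5.0% | 5.0% |
| Power, odds ratio 0.65, share 42% | pooled | 78% | 75% | 63% |
| | conditional | 81% | 81% | 77% |
| | CMH | 82% | 82% | 81% |
| Power, odds ratio 0.65, share 37.5% | pooled | 81% | 79% | 73% |
| | CMH | 83% | 82% | 82% |

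(Columns are assumed juice use at 15 months.) With the 15-month share at 25% instead, false claims of benefit (nominal 2.5%) are 3.9 / 5.0 / 7.7% pooled and 2.5 to 2.6% with CMH. The calendar alone gives a pooled type I error of 5.2 to 5.8%. The 10-point shift gives 7.2% (mild gradient) to 19.5% (steep).

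**4. At the plan's own effect.** Odds ratio (0.20/0.80)/(0.48/0.52) = 0.27. At 375 per group, power is 100% by every method. At 44 per group and share 42%, pooled and CMH power are 80% and 81% (15-month use 60%), or 75% and 80% (70%).

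**5. Cost when there is no age gradient.** At 375 per group: 0.1 to 0.4 points of power, 1.3 at a 50% share, and 79.2 − 76.2 = 3.0 under a 20-point shift. At 44 per group: 81.9 − 79.7 = 2.2 with an equal mix, and 81.1 − 76.7 = 4.4 under a 20-point shift.

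**6. What the simulation leaves out.** It treats surveys as independent. Suppose a fraction f of 125 nine-month respondents per group also answered at 6 months, with within-parent correlation ρ (both assumed). The variance is multiplied by 1 + 2f × 125ρ/375. For f = 0.5 and ρ = 0.3 this is 1.10, and the type I error is P(|Z| > 1.96/√1.10) = 6.2%. For f = 1 and ρ = 0.7 it is 1.467, giving 10.6%. Simulation of CMH gave 6.5 to 11.0%. The pooled test has the same problem.

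**The case against.** The strongest reply is that the plan already covers this. Child age can be read as a demographic, and differences are to be assessed and controlled for. On that reading the conditional rows above show most of the protection recovered at a 42% share: at 55 to 60% use, about 0.2 points of type I error and 1 point of power remain. The amendment entry also shows that stratified analysis is intended, though for intervention exposure and response rates, not visit. This stands as a reason to keep the point modest. The wording permits the adjustment without requiring it, and a significance screen can miss an imbalance that still matters.

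Second, the larger figures combine an assumed mix with an assumed 15-month prevalence. That is correct. Section 6 also speaks of intake, which is not the same as the percentage of parents giving any juice.

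Third, part of the gap between methods is not due to visit mix. With no age gradient the pooled test already rejects in 5.2 to 5.3% of trials, so about 0.25 points of each type I difference belong to the test itself.

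Fourth, the 5.0% for CMH depends on independent surveys, and main-study parents cannot be linked. That limits the claim made for the remedy, but it does not favour pooling, which shares the defect.

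A reader might infer that the juice comparison is biased, or that Appendix A builds in a serious imbalance. The documents support neither. No unequal mix is reported, the 6- and 15-month surveys have three months in each period, and the shorter 9-month window in the intervention period shifts the estimate by under 1 point.

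**Conclusion.** The point holds as a conditional risk with a better method available. Section 16 does not fix survey visit in the main juice comparison, although the plan itself describes juice intake as rising with age. Bias needs two things together: pooled visits whose mix differs between periods, and prevalence that varies by visit. The documents support the second in direction only and report nothing on the first.

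Under moderate assumptions the shift is 0.6 to 1.9 points, with a power loss of about 4 to 18 points at an odds ratio of 0.65. Steeper assumed gradients give up to 4.0 points for a 10-point change in mix. Significance at 48% versus 20% with 375 per group is not threatened. What is at stake is a smaller true effect, and the size of the estimate passed to the later trial. Stratifying by visit does not correct calendar-time confounding or repeat respondents.

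**What to change.** - Make the main juice comparison a Cochran-Mantel-Haenszel test, or a logistic regression with survey visit as a stratum, regardless of observed imbalance. Add demographic covariates in the model where needed. Keep the unadjusted chi-squared test as supportive.
- Report a visit-adjusted risk difference. Treat the awareness outcome the same way for consistency; no age trend is documented for it, and it was not simulated.
- Give visit-specific estimates descriptively. The video shown and child age are confounded across visits, so these do not separate the two videos.
- Confirm that each survey records its visit. Appendix A implies this but no section states it.
- State that the analysis treats surveys as independent, and that stratification does not address parents who answer at more than one visit or changes over calendar time.
- Separately, reconcile Section 5 (6 and 15 months) with Sections 1 and 6 and Appendix A (6, 9 and 15 months) on which visits supply the outcome.

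This is a cheap change of analysis wording and needs no extra participants. The price is the small loss of power in step 5 of the working, which arises if juice use does not vary with age.
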